**LIST OF ABBREVIATIONS AND DEFINITIONS OF TERMS**

Abbreviation	Definition
active control arm	Comirnaty (tozinameran, BNT162b2, Pfizer/BioNTech) SARS-CoV-2 vaccine
AE	adverse event
AESI	adverse event of special interest
ATC	Anatomic-Therapeutic-Chemical Class
active trial phase	The time from the trial vaccination up to and including the end of active trial phase visit at 28 to 35 days after trial vaccination
BN	Bavarian Nordic
BMI	body mass index
CDC	Centers for Disease Control
CI	confidence interval
completed primary plus boost vaccination	Completed primary plus boost vaccination with locally authorized SARS-CoV-2 vaccine(s). “Completed primary plus boost vaccination” includes full primary vaccination as described below, plus a boost vaccination administered at least 2 months after the last primary dose. The boost dose may be the same or different vaccine as received in the primary vaccination regimen.
completed primary vaccination regimen	Completed primary vaccination regimen with a locally authorized SARS-CoV-2 vaccine. “Completed primary vaccination regimen” includes full primary vaccination as described in the labeling of the initial vaccine, with no less than 3 weeks between the doses; completed primary vaccination also includes any mix/match series of 2 doses of any locally authorized SARS-CoV-2 vaccine, or a single dose of any locally authorized COVID-19 vaccine in subjects who previously had a confirmed COVID-19 infection.
CSR	clinical study report
CTS	clinical trial site
Cohort 1	adult subjects who previously completed primary vaccination for SARS-CoV-2
Cohort 2	adult subjects who have completed primary vaccination for, and received 1 booster dose, of SARS-CoV-2 vaccine
COVID-19	coronavirus disease 2019
DMC	data monitoring committee
ECG	electrocardiogram
EDC	electronic data capture
EAP	End of active trial phase. The visit (Visit 4) at the end of the active trial phase, approximately 28 to 35 days after trial vaccination. In the event of early withdrawal of a subject from the trial during the active trial phase, the EAP visit will be the visit at which the final safety endpoints for the trial are collected.
ELISpot	enzyme-linked immunospot assay

Abbreviation	Definition
ELISA	enzyme-linked immunosorbent assay
FCS	fully conditional specification
FU	follow up
FU Phase	The time after the active trial phase, up to approximately 6 months after trial vaccination.
FDA	food and drug administration
GCP	good clinical practice
GMT	geometric mean titer
GMFI	geometric mean fold increase
IAS	Immunogenicity Analysis Set
ICF	informed consent form
ICH	International Conference on Harmonization
LLOD	lower limit of detection
LLOQ	lower limit of quantitation
LS means	Least squares means
Max	maximum
MedDRA	Medical Dictionary for Regulatory Activities
MI	multiple imputation
Min	minimum
mRNA	messenger ribonucleic acid
Part A	randomized, double-blind, active controlled component of the trial
Part B	open-label, single-arm component of the trial
PBMC	peripheral blood mononuclear cells
PCR	polymerase chain reaction
PI	principal investigator
PT	Preferred Term
SAE	serious adverse event
SAP	statistical analysis plan
SARS-CoV-2	severe acute respiratory syndrome coronavirus 2
index virus	Wuhan wild type isolate of SARS-CoV-2
SD	standard deviation
SDTM	Study Data Tabulation Model

Abbreviation	Definition
SFU	spot forming units
SI	Système International d'Unités
SOC	System Organ Class
SPEAC	Safety Platform for Emergency vACCines
trial phase	The active trial phase plus the follow up phase.
trial vaccination	Part A, randomized component: single dose of 100 µg ABNCoV2 or a single 30 µg dose of Comirnaty Part B, single-arm component: Single 100 µg dose of ABNCoV2
ULOQ	upper limit of quantitation
VOC	SARS-CoV-2 variants of concern
WHO	World Health Organization
WHO Drug	World Health Organization Drug Dictionary

## 1. INTRODUCTION

This Statistical Analysis Plan (SAP) details the statistical methodology to be used in analyzing trial data and outlines the key statistical programming specifications. It describes the variables and populations, anticipated data transformations and manipulations, and other details of the analyses not provided in the trial protocol. The SAP is written based on recommendations from *ICH E3: Structure and Content of Clinical Study Reports* and *ICH E9: Statistical Principles for Clinical Trials*. Table, figure, and listing specifications are contained in a separate document.

Deviations from the current protocol are described in Section 4.8. If any unforeseen additional analyses are included in the clinical study report (CSR), they will be clearly described as additional, unplanned analyses in Section 4.8 if added prior to database lock or in the equivalent section of the CSR if ad-hoc analyses are requested post-database lock.

### 1.1. Objectives, Endpoints, and Estimands

**Table 1: Objectives and Endpoints**

Objectives	Endpoints
Primary	
Part A: To assess non-inferiority, or superiority, of vaccination with ABNCoV2 compared to Comirnaty in terms of neutralizing antibodies against the SARS-CoV-2 index virus (Wuhan wild type isolate), in Part A Cohort 1 (adult subjects who previously completed primary vaccination at least 3 months prior to the screening visit) and Part A Cohort 2 (adult subjects who have completed primary vaccination and have received 1 booster vaccination).	Part A: Geometric mean titer (GMT) of neutralizing antibodies against the SARS-CoV-2 index virus at 2 weeks after trial vaccination, in each Part A cohort.
Key Secondary	
Part A: To assess in Part A cohorts the non-inferiority, or superiority, of vaccination with ABNCoV2 compared to Comirnaty in terms of neutralizing antibodies against SARS-CoV-2 variants of concern (VOCs) circulating at time of the trial.	Part A: GMT of neutralizing antibodies against the SARS-CoV-2 VOCs circulating at time of the trial, at 2 weeks after trial vaccination, in the Part A cohort(s) in which the primary endpoint success criterion is met.
Other Secondary	
Part B: To assess neutralizing antibody titers against the SARS-CoV-2 index virus after vaccination with ABNCoV2 in the immunogenicity subsets of Part B Cohort 1 and Cohort 2.	Part B: GMTs of neutralizing antibodies against the SARS-CoV-2 index virus at 2 weeks after trial vaccination in subjects receiving ABNCoV2 in the immunogenicity subsets of Part B Cohort 1 and Cohort 2.

Objectives	Endpoints
Safety Objectives	

Part A: To assess the safety and tolerability of the ABNCoV2 vaccine compared to Comirnaty in previously vaccinated adult subjects in Part A (both cohorts).
 
Parts A and B: To assess the safety and tolerability of the ABNCoV2 vaccine in previously vaccinated adult subjects (all subjects receiving ABNCoV2).
	
Part A: For all subjects receiving ABNCoV2 compared to those receiving Comirnaty, the percent who report the safety endpoints listed below.
 
Parts A and B: For all subjects receiving ABNCoV2, the percent who report the safety endpoints listed below.
 
 
• Serious adverse events (SAEs) or adverse events of special interest (AESIs) assessed as related to trial vaccine during the entire trial phase, which includes both the active trial phase and follow-up.
 
• Grade 3 or higher adverse events (AEs) assessed as related to trial vaccine in the 8-day period starting with the day of vaccination.
 
• SAEs, AESIs, or medically attended AEs (MAAEs), regardless of relationship, during the active trial phase.
 
• SAEs, AESIs, or MAAEs, regardless of relationship, during the entire trial phase.
 
• Grade 3 or higher AEs assessed as related to trial vaccine during the active trial phase.
 
• Solicited local AEs in the 8-day period starting with the day of vaccination.
 
• Solicited general AEs in the 8-day period starting with the day of vaccination.
 

Exploratory Objectives	

To compare total binding immunoglobulin G (IgG) antibodies against the SARS-CoV-2 index virus after vaccination with ABNCoV2 or Comirnaty in subsets of each Part A cohort.
	
GMT of total binding IgG antibodies against the SARS-CoV-2 index virus at 2 weeks after trial vaccination in subsets of each Part A cohort.
 
Geometric mean fold increases, from baseline to post-baseline time points after trial vaccination, in total binding IgG antibodies

Objectives	Endpoints
	against the SARS-CoV-2 index virus in subsets of each Part A cohort.
To explore the kinetics of SARS-CoV-2-specific humoral responses in subsets of each Part A cohort.	
Geometric mean fold increases, from baseline to post-baseline time points after trial vaccination, in neutralizing antibodies against the SARS-CoV-2 index virus.
 
Geometric mean fold increases, from baseline to post-baseline time points after trial vaccination, in neutralizing antibodies against the SARS-CoV-2 VOCs circulating at time of the trial.
 
GMT of neutralizing antibodies against the SARS-CoV-2 index virus and the SARS-CoV-2 VOCs circulating at time of the trial, at 1, 4, 13 and 26 weeks after trial vaccination in subsets of each Part A cohort.

To compare neutralizing antibodies against the SARS-CoV-2 index virus at 2 weeks after vaccination with ABNCoV2 between cohorts in Part A and Part B.	GMTs and geometric mean fold increases, from baseline to post-baseline time points after trial vaccination, in neutralizing antibodies against the SARS-CoV-2 index virus at 2 weeks after trial vaccination.
To explore SARS-CoV-2-specific cellular responses at 1 week after ABNCoV2 vaccination within the immunogenicity subsets of each Part B cohort.	Geometric means of SARS-CoV-2-specific T cells secreting interferon-g / interleukin-4 at 1 week after ABNCoV2 vaccination within the immunogenicity subsets of each Part B cohort.

AE = adverse event, AESI = adverse event of special interest, GMT = geometric mean titer, IgG = immunoglobulin G, MAAE = medically attended adverse event; SAE = serious adverse event, VOC = SARS-CoV-2 variants of concern.

### Primary Estimand

The primary variable of interest is the subjects' neutralizing antibody result against the SARS-CoV-2 index virus measured at 2 weeks after trial vaccination in each Part A cohort, and the variable will be summarized as the ratio of geometric means for ABNCoV2 compared to Comirnaty in subjects meeting the Immunogenicity Analysis Set (IAS) definition.

The planned primary analysis will be conducted in each of the Part A cohorts, and the null hypothesis of inferiority will be rejected if the ratio of GMTs is within the non-inferiority margin of 0.67, i.e., the lower limit of the 2-sided 97.5% CI of the GMT ratio is  $\geq 0.67$ .

The following are considered intercurrent events:

1. Development of COVID-19 symptoms and having a positive test for SARS-CoV-2 infection prior to Visit 3 (12 to 16 days after vaccination) by PCR or other testing method,

2. Administration of a booster for SARS-CoV-2 prior to Visit 3, and
3. Discontinuation from the trial due to AEs.

For the primary estimand, the third intercurrent event is not considered as having an impact on the SARS-CoV-2 neutralizing antibody levels and therefore the “treatment policy” strategy will be used. Exposure to the virus or receiving another booster vaccine can have significant effect on SARS-CoV-2 neutralizing antibody levels, and thus subjects who develop intercurrent infections will be excluded from the primary analysis. This is equivalent to the “while on treatment” strategy. Prior to database lock, a data review meeting will determine if any other intercurrent events (e.g., protocol violations) would affect the primary immunogenicity outcome. Strategies to handle these additional intercurrent events will be determined in a blinded fashion.

### Secondary Estimand

The key secondary variables of interest are the subjects’ neutralizing antibody titers against circulating SARS-CoV-2 VOCs measured at 2 weeks after trial vaccination in Part A, and they will be summarized as the ratios of GMTs for ABNCoV2 compared to Comirnaty.

The null hypothesis of inferiority will be rejected if the ratio of GMTs against the SARS-CoV-2 VOCs, for ABNCoV2 vaccine compared to Comirnaty vaccine, is within the non-inferiority margin of 0.67. Only Part A cohort(s) that meet the primary success criterion will be formally tested for non-inferiority of ABNCoV2 to Comirnaty for each VOC, and a Bonferroni correction will be used to control the overall type I error rate for the trial.

The intercurrent events for the secondary analyses are the same as for the primary analysis and will be handled in a similar fashion.

## 1.2. Trial Design

Details of the trial design are listed in [Table 2](#).

**Table 2: Details of Trial Design**

Design Element	Description
Study phase and study population	Phase 3, healthy adult subjects previously vaccinated for SARS-CoV-2
Design type	Part A: Parallel Part B: Single arm
Control Method	Part A: Active controlled, Comirnaty Part B: None
Blind level	Part A: Double blind Part B: Open label
Method of Assignment	Part A: Randomized 1:1 to a single dose of ABNCoV2 or Comirnaty, stratified by age group (<65 years vs. ≥65 years) and prior vaccination regimens, within each cohort. Part B: Non-randomized, all assigned to a single dose of ABNCoV2

Design Element	Description
Duration of Trial Participation	Screening: 2 Weeks Active Trial Phase: 4 Weeks Follow-up: 22 Weeks
Dose Adjustment Rules	Not applicable, single dose given on Day 1
Planned Interim Analyses	No interim analysis of immunogenicity is planned; however, a data monitoring committee will review cumulative safety data throughout the trial. No immunogenicity data will be reviewed prior to the primary analysis.
Timing of Primary Analysis	The primary analyses of immunogenicity and analyses of safety will be performed once all subjects within a trial part have completed the 8-week Follow-up 1 visit. Data will be cleaned through the 8-week timepoint. A data review meeting will be conducted to review the key trial data and determine if strategies to handle other intercurrent events are needed in addition to the strategies to handle the planned intercurrent events in a blinded manner. Treatment assignment will not be unblinded for the primary analyses until the data are locked and analysis populations and strategies to handle intercurrent events are set.
Timing of Subsequent Analyses	Follow-up analyses will be performed once all subjects have completed the 3 month and the 6 month follow-up visits, respectively. The final analysis for the trial will occur once all subjects have completed all follow-up or have withdrawn early from the trial and the database has been locked.

## 2. STATISTICAL HYPOTHESIS

In Part A of the trial, the non-inferiority of ABNCoV2 will be assessed in comparison with Comirnaty in terms of neutralizing antibodies against the SARS-CoV-2 index virus and circulating VOCs. The hypothesis will be tested in the randomized, double-blind component, in Cohort 1 (adult subjects who previously completed primary vaccination only) and Cohort 2 (adult subjects who have received 1 booster vaccination after a primary regimen) simultaneously. If the non-inferiority margin is met, superiority comparison will be carried out in the same cohort with the same type I error level.

No hypothesis testing is planned for the open-label, single-arm Part B of the trial.

### 2.1. Multiplicity Adjustment

The hypothesis test of non-inferiority of ABNCoV2 to Comirnaty in terms of neutralizing antibody titers for SARS-CoV-2 will be performed in Part A in up to 2 cohorts. A Bonferroni correction will be used to control the trial-wide type I error of  $\alpha = 0.025$ , one-sided. In the event a cohort does not meet the requirement of 400 evaluable subjects for the primary endpoint analysis, summaries for the under-enrolled cohort will be considered purely descriptive.

The key secondary endpoints, ratios of GMTs for the VOCs at 2 weeks after trial vaccination, will be formally tested in Part A for non-inferiority of ABNCoV2 to Comirnaty only in the cohort(s) in which the primary success criterion is met. If the primary success criterion is met in only one cohort, VOCs will be formally tested in that cohort only. A Bonferroni adjustment will be used such that each VOC non-inferiority hypothesis will be tested at the  $\alpha =$

$\frac{0.025}{\text{number of VOCs tested}}$  level. For example, if 3 VOCs are tested, each test will be performed at the

$\alpha = 0.0083$  level such that success would require the lower bound of a 98.3% CI to be at least 0.67. In the event that success criteria are met for both Cohort 1 and Cohort 2, the number of tests will multiply, and thus non-inferiority hypothesis will be tested at the  $\alpha =$

$\frac{0.0125}{\text{number of VOCs tested}}$  level so that the overall type I error rate will be no more than 5%.

Due to the challenges of finding non-boosted potential trial subjects during enrollment, Cohort 1 was under-enrolled for the primary analysis, even with extension of the enrollment period. Therefore, only Cohort 2 will be formally tested.

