	To compare neutralizing antibodies against the SARS-CoV-2 index virus at 2 weeks after vaccination with ABNCoV2 between cohorts in Part A and Part B.	
Primary Endpoint Population-level Summary	Part A: Geometric mean titer (GMT) of neutralizing antibodies against the SARS-CoV-2 index virus at 2 weeks after trial vaccination, in each Part A cohort.	
Success Criterion for Primary Endpoint	If the sample size requirement is met in each of the Part A cohorts (minimum of 400 evaluable per cohort), the success criterion will be applied in each of the cohorts as specified below. In the event the sample size requirement is not met in one of the cohorts, the success criterion will only be applied to the cohort meeting the sample size requirement, and results for the under-recruited cohort will be descriptive only.	
	Ratio of GMTs at 2 weeks after trial vaccination, for ABNCoV2 vaccine compared to Comirnaty vaccine, is within the non-inferiority margin of 0.67; specifically, the success criterion will be met within each cohort if the lower bound of the 2-sided 97.5% CI of the GMT ratio is \geq 0.67.	
	If the non-inferiority criterion is met, a superiority test will be carried out based on the same type I error level.	

ABNCoV2-03

Edition 8.0

	If the non-inferiority criterion is met in at least one cohort, supportive analyses will include assessing non-inferiority or superiority in Cohort 1 and Cohort 2 combined.	
Key Secondary Endpoint Population- level Summary	Part A: GMT of neutralizing antibodies against the SARS-CoV-2 VOCs circulating at time of the trial, at 2 weeks after trial vaccination, in the Part A cohort(s) in which the primary endpoint success criterion is met.	

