### 4.2.2. Main Analytical Approach

The estimate of the primary estimand will be created using the IAS.

The geometric mean, 95 % CI, median, minimum, and maximum of SARS-CoV-2 neutralizing antibody results for Part A will be calculated within each cohort. Additionally, in Part A, the ratios of the GMTs between ABNCoV2 and Comirnaty will be provided along with p-values, 95% CI and 97.5% CI from a generalized linear model. Age and baseline neutralizing antibody results will be included as covariates in the model to compare between the vaccination arms. The Least Squares (LS) Means and CIs from the model will be back transformed to their original scale.

GMTs will be obtained by computing the arithmetic means and the corresponding 95% CIs on the  $\log_{10}$  scale, and then exponentiating the  $\log_{10}$  means and confidence limits to return the results to the original scale.

Figures of neutralizing antibody results with the GMT and fold increase for the index virus and each VOC will be plotted by cohort, and for both cohorts combined, for each vaccination arm in Part A.

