## 5. SAMPLE SIZE DETERMINATION

### 5.1. Part A

The primary and key secondary analyses are planned to be tested in the randomized, double-blind component of the trial (Part A) in both Cohort 1 and Cohort 2. Two non-inferiority tests are planned. Therefore, the sample size calculation is based on a 1-sided, 0.0125 type I error,  $\alpha$ , to control for both tests. This will maintain the trial-wide  $\alpha$  at 0.025 for the 1-sided null inferiority hypotheses.

Based on data from the ABNCoV2 phase 2 trial, we assume the common standard deviation to be 0.52 for  $\log_{10}$  transformed neutralizing antibody results. The test of non-inferiority of ABNCoV2 compared with Comirnaty will be performed by comparing the lower end of the 97.5% CI with a non-inferiority margin of 0.67 in the ratio of neutralizing antibody GMTs between the 2 arms. We further assume a 10% non-evaluable rate due to dropouts or invalid samples. With an evaluable sample size of 450, a 1-sided test with an  $\alpha$  of 0.0125 will have approximately 90% power to reject the null hypothesis that ABNCoV2 is inferior to Comirnaty.

A minimum sample size of 400 evaluable subjects will be required for the non-inferiority hypothesis test to be performed for the primary endpoint within each cohort. In the event the evaluable sample size is as low as 400, the power to reject the null hypothesis that ABNCoV2 is inferior to Comirnaty is approximately 86%. If the minimum sample size is not met in 1 of the cohorts regardless of recruitment effort, data from the cohort will be summarized descriptively and will be integrated in the combined-cohort analyses.

For the key secondary analyses, the number of hypothesis tests to be performed will depend on the number of VOCs with immunogenicity results available. VOCs will only be formally tested sequentially in the separate Part A cohorts and in the 2 cohorts combined.

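### With only Cohort 2 left to test, the primary criterion still uses the 97.5% CI set for two tests, so half of the one-sided 0.025 goes unused on the primary test: a loss of efficiency, not of validity

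*SAP*

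**What the plan says.** SAP 2.1 sets the trial-wide one-sided error at 0.025 for non-inferiority tests in up to two Part A cohorts: "A Bonferroni correction will be used to control the trial-wide type I error of" that value. The same section then reports the enrolment shortfall in Cohort 1 and ends: "Therefore, only Cohort 2 will be formally tested".

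The per-test level comes from SAP 5.1: "Two non-inferiority tests are planned. Therefore, the sample size calculation is based on a 1-sided, 0.0125 type I error". Protocol 12.2.1 gives the same reasoning.

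The decision rule is in SAP 1.1 (Primary Estimand). Inferiority is rejected if "the lower limit of the 2-sided 97.5% CI of the GMT ratio is" at least 0.67. Protocol 1.3, 5.1, 12.6.1 and 12.6.2 carry the same criterion. SAP 4.2.2 plans p-values together with the "95% CI and 97.5% CI from a generalized linear model" and does not say which interval decides.

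The protocol foresaw a short cohort. Its synopsis says that in that case "the success criterion will only be applied to the cohort meeting the sample size requirement". Protocol 5.1 repeats this, and neither place changes the confidence level.

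Superiority follows non-inferiority at the same type I error level (Protocol 4.1, SAP 2). If only one cohort succeeds, SAP 2.1 tests the variants of concern (VOCs) at 0.025 divided by the number of VOCs.

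**The concern.** The sole reason given for 0.0125 is that there would be two tests. SAP 2.1 removes one of them, but the criterion in SAP 1.1 and the derivation in SAP 5.1 were left as they were. The SAP neither moves the other 0.0125 to Cohort 2 nor says that it is deliberately given up, and its list of changes (SAP 4.8) does not mention the matter.

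Two things are at stake. First, the primary test is stricter than the stated error rate requires, and its failure closes the whole key secondary family, because VOCs are tested only where the primary succeeds. Second, the texts can be read two ways. A Bonferroni correction over one tested cohort gives 0.025, that is a 95% CI, while SAP 1.1 says 97.5% and SAP 4.2.2 outputs both.

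**Working it through.** **Inputs.** Margin 0.67, SD 0.52 on the log10 scale, 450 evaluable (minimum 400), per-test one-sided level 0.0125 (all SAP 5.1); 1:1 allocation (SAP 1.2); trial-wide one-sided level 0.025 (SAP 2.1). Assumption: true GMT ratio 1.0. The documents do not state it, but it reproduces their power figures.

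**Alpha used.** Planned: 0.0125 + 0.0125 = 0.025. With Cohort 2 alone: 0.0125. Unused on the primary test: 0.025 − 0.0125 = 0.0125, or half.

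**Formula.** Power = Φ(δ/SE − z), with δ = −log10(0.67) = 0.1739 and SE = 0.52 × √(2/n per arm). The critical value z is 2.2414 at 0.0125 and 1.9600 at 0.025.

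- 450 evaluable (225 per arm): SE = 0.0490, δ/SE = 3.548
- 400 evaluable (200 per arm): SE = 0.0520, δ/SE = 3.345

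**The plan's figures first.** At 0.0125, Φ(3.548 − 2.241) = 90.4% and Φ(3.345 − 2.241) = 86.5%. The stated values of about 90% and 86% reproduce.

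**At the full 0.025.** The smallest observed ratio that passes is 0.67 × 10^(z × SE).

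| Evaluable | Power at 0.0125 | Power at 0.025 | Smallest passing ratio, 97.5% CI | Smallest passing ratio, 95% CI |
|---|---|---|---|---|
| 450 | 90.4% | 94.4% | 0.863 | 0.836 |
| 400 | 86.5% | 91.7% | 0.876 | 0.847 |

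The gain is about 4 points at 450 and 5 points at 400. A noncentral t calculation gives nearly the same (90.3% and 94.3%; 86.3% and 91.6%). At 450, an observed ratio between 0.836 and 0.863 would pass on one interval and fail on the other.

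**If the true ratio is below 1 (assumed values, 450 evaluable).** At 0.95, power is 80.3% versus 87.1%. At 0.90, it is 64.5% versus 74.4%.

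**With baseline titer in the model.** The planned model adjusts for age and baseline titer, which the figures above ignore. The documents give no correlation between baseline and Week 2. If it were 0.3 to 0.5, with residual SD = 0.52 × √(1 − r²), power at 450 would be 93.0% to 96.8% at 0.0125 and 96.1% to 98.4% at 0.025. The gain shrinks to about 3.0 to 1.5 points.

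**VOC levels with one successful cohort.** One VOC: 0.025. Two: 0.025/2 = 0.0125. Three: 0.025/3 = 0.0083.

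**The case against.** The strongest reply is that nothing was forgotten. The protocol names this contingency and applies the same criterion to the remaining cohort, so the SAP is faithful to it. Protocol Edition 8.0 (30 June 2023) postdates SAP 1.0 (19 May 2023), in which the shortfall is already recorded. It amended the primary estimand section and left 97.5% in place. A sponsor may reasonably decline to loosen a phase 3 non-inferiority criterion after enrolment has closed. All of this stands, and it makes the point one of efficiency.

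Several stronger readings are tempting but not supported:

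- A reader might infer that error control is broken or that the SAP departs from the protocol. Neither is so: a 97.5% CI for a single test is conservative, and it is the pre-specified rule.
- A reader might infer that Cohort 2 is now underpowered. Losing Cohort 1 takes no power from Cohort 2. The extra 4 to 5 points would lie above the design target.
- A reader might infer that half of the trial's alpha is never used. The unused half concerns the index-virus non-inferiority test and its linked superiority test. The VOC family receives the full 0.025 once one cohort succeeds.
- A reader might infer that the secondary tests are easier than the primary that gates them. That holds only with exactly one VOC. With two the levels are equal, and with three, the SAP's own example, the VOC tests are stricter. The number of VOCs is not stated.

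It is also fair to object that a bare move to 0.025 would relax the superiority test as well. The fix has to deal with that.

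**Conclusion.** The point holds as an avoidable loss of efficiency, with some ambiguity about the deciding interval. One test remains and uses 0.0125 of a stated one-sided 0.025. Cohort 1 left formal testing under a pre-specified size rule of 400 evaluable subjects, and the SAP attributes the shortfall to difficulty in finding non-boosted subjects. SAP 1.2 says that no immunogenicity data are reviewed before the primary analysis and that unblinding follows the lock. Testing Cohort 2 at 0.025 would therefore keep the error of the primary non-inferiority claim at the stated level.

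The gain is about 4 points of power at 450 evaluable and 5 at 400, given an SD of 0.52, a true ratio of 1.0 and no covariate adjustment. It may be smaller at 450 once baseline titer is in the model, and larger if the true ratio is below 1. Cohort 2's evaluable number is not in the documents, so 400 to 450 is an assumed range. Keeping 97.5% would remain valid.

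**What to change.** Before unblinding, amend the protocol (synopsis, 5.1, 12.6.1, 12.6.2) and revise SAP 1.1, 2.1, 4.2.2 and 5.1 as follows:

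- When only one cohort qualifies for formal testing, non-inferiority is decided by the lower limit of the two-sided 95% CI being at least 0.67 (one-sided 0.025).
- State the level of the follow-on superiority test explicitly. Under the present wording it would move to 0.025 by default.
- Keep the 97.5% CI as a supportive result, and name the deciding interval in SAP 4.2.2.
- In SAP 5.1, say that one primary test remains.

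The cost is a short amendment; the 95% CI is already planned output. The downside is a criterion less strict than the one first announced, so the amendment should record that the change rests only on enrolment counts and was made blinded. If the sponsor prefers to keep 97.5%, one sentence saying that it is deliberately retained and is the deciding interval would at least remove the ambiguity.
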